6 HANDLING OF MISSING DATA

No imputation will be considered for incomplete data except the following:

- In order to classify medications as concomitant or prior medications, the incomplete stop date for any medication will be imputed as follows:
 - If the year is missing, then the stop date will not be imputed;
 - If both day and month are missing but year is not missing, if the year is prior to the year of C1D1, then the stop date will be imputed as 01/July, otherwise if the year is the same as the year of C1D1, then the stop date will be imputed as 01/January;
 - If the day is missing but the month and year are not missing, and the month and year is the same as C1D1, then the stop date will be imputed as the date of C1D1, otherwise if the month and year is prior to C1D1, then the stop date will be imputed as first day of the month.
- In order to determine the time from last systemic therapy to informed consent, the incomplete stop date for the last systemic therapy will be imputed as follows:
 - If the year is missing, then the stop date will not be imputed;
 - If both day and month are missing but year is not missing, if the year is prior to the year of informed consent, then the stop date will be imputed as 01/July, otherwise if the year is the same as the year of informed consent, then the stop date will be imputed as 01/January;
 - If the day is missing but the month and year are not missing, then the stop date will be imputed as first day of the month.
- In order to determine the duration of last systemic therapy, the incomplete start date for the last systemic therapy will be imputed as follows:
 - If the year is missing, then the stop date will not be imputed;
 - If both day and month are missing but year is not missing, if the year is prior to the year of informed consent, then the start date will be imputed as 01/July, otherwise if the year is the same as the year of informed consent, then the stop date will be imputed as 01/January;
 - If the day is missing but the month and year are not missing, then the start date will be imputed as first day of the month.

- In order to determine the time from initial diagnosis of primary cancer to informed consent and time from initial metastasis diagnosis or most recent local recurrence to informed consent, the incomplete date of diagnosis will be imputed as follows:
 - If the year is missing, then the date of diagnosis will not be imputed;
 - If the day is missing but the month and year are not missing, then the date of diagnosis will be imputed as the first day of the month;
 - If both day and month are missing and the year is prior to the year of informed consent, then the date of diagnosis will be imputed as 01/July, otherwise if the year is the same as the year of informed consent, then the date of diagnosis will be imputed as 01/January.

- In order to determine the duration of AEs, an incomplete start date of any AE will be imputed as follows:
 - If both month and year are missing, then they should be queried and the missing start date of the AE will not be imputed;
 - If start day of the AE is missing but month and year are not missing:
 - If the month of occurrence of the AE is after the month of C1D1, then the missing day will be imputed as the first day of the month;
 - If the month of occurrence of the AE is the same as the month of C1D1, then the missing date will be imputed as the same date of C1D1;

- In order to determine the duration of AEs, incomplete stop date of any AEs will be imputed as follows:
 - If the stop date of any AE is missing but the month and year are not missing, then the stop date will be imputed as last day of the month or the date of discontinuation from the study whichever is the earlier;
 - If both stop date and month of any AE are missing but year is present, then the stop date will be imputed as 31/December or the date of discontinuation from the study, whichever is earliest;
 - If the stop date for any AE is completely missing, then the date will be imputed as date of discontinuation from the study.

7 ANALYSIS POPULATIONS

Safety Population: all subjects who receive at least one dose (or partial dose) of study treatment will be included in the analysis of safety.

DLT Population: all subjects who complete at least one cycle of treatment or discontinue from the study treatment due to DLT will be included.

Pharmacokinetic Population: all subjects in the Safety Population who have relatively complete individual analyte concentration-time profiles that allow for the computation of meaningful PK parameter values.

Response Evaluable Population: subjects who met all eligibility criteria, have measurable disease (per Response Evaluation Criteria in Solid Tumors [RECIST) 1.1) at baseline, and also have at least one post-baseline assessment of tumor response.

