Statistical Methods:	Safety: The primary safety analyses will include incidence of DLTs by dose cohort. Safety analyses will summarize the incidence, grade and duration of toxicities according to the National Cancer Institute Common Terminology Criteria for AEs (NCI-CTCAE), version 4.03. All AEs will be listed and tabulated by system organ class, preferred term, and coded according to the Medical Dictionary for Regulatory Activities

	
(MedDRA). The incidence of AEs will be tabulated and reviewed for potential significance and clinical importance. Vital signs (including change in weight) and clinical laboratory test results will be listed and summarized descriptively by dose (for the dose escalation phase) and by tumor type (for the dose expansion phase). Any significant physical examination findings will be listed. ECG data will be evaluated by central review. Abnormalities, if present, will be listed. A separate listing and summary of all immune-related AEs (irAEs) will be provided.
 
Efficacy:
 
Efficacy assessments will be summarized separately for the dose escalation and dose expansion cohorts. In order to assess preliminary efficacy, the primary efficacy outcome measurement ORR, and the secondary efficacy outcomes, BOR, CBR, and TTR, will be tabulated by dose and tumor type. [REDACTED]
 
[REDACTED] Individual tumor measurements, tumor size and percent changes in tumor size will be listed. Changes in tumor size will be presented graphically for each specific tumor type. ORR and BOR will each be estimated based on the response evaluable population which is defined as subjects with measurable disease at baseline who receive the study drug and also have one post-baseline assessment of tumor response or are withdrawn due to progressive disease/death prior to first response assessment. DOR will be estimated for subjects who achieve complete response (CR) or partial response (PR). Other secondary efficacy analyses will be based on the all treated population and may be done for the response evaluable population as sensitivity analyses.
 
Pharmacokinetic parameters will be tabulated and summarized with descriptive statistics by dose level. Values for biomarker expression will be calculated at each observation time. Changes in expression from screening to each observation time will be assessed.

--	---

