### 10.4 Analysis Sets

Safety Population: All subjects who receive at least one dose (or partial dose) of study treatment will be included in the analysis of safety.

DLT Population: All subjects who complete at least one cycle of treatment or discontinue from the study treatment due to DLT will be included.

Pharmacokinetic Population: All subjects in the Safety Population who have relatively complete individual analyte concentration-time profiles that allow for the computation of meaningful PK parameter values.

Response Evaluable Population: Subjects who have measurable disease (per RECIST 1.1) at baseline and also have one post-baseline assessment of tumor response or are withdrawn due to progressive disease/death prior to first response assessment.

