### 10.5.3 Efficacy

The efficacy outcomes will include:

1. objective response rate (ORR)
2. best overall response (BOR)

■ [REDACTED]

4. duration of response (DOR)

5. clinical benefit rate (CBR)

6. time to response (TTR)

■ [REDACTED]

The primary efficacy measurement will be ORR per RECIST v1.1 based on the Response Evaluable population by tumor type. The number and proportion of subjects with objective tumor response (CR and PR) will be calculated based on number of subjects with measurable disease at baseline. Ninety-five percent (95%) confidence interval (CI) will also be calculated using exact binomial method. Data listing for tumor assessments and tumor response will be provided.

A secondary measurement will be BOR per RECIST v1.1 based on the Response Evaluable population by tumor type. The number and proportion of subjects with a best overall response of CR or PR will be calculated based on number of subjects with measurable disease at baseline. Ninety-five percent (95%) CI will also be calculated using exact binomial method.

DOR will be defined as the time from first documented CR or PR until the earliest evidence of disease progression, new subsequent anti-cancer therapy, or death from any cause. DOR will be estimated using Kaplan-Meier method for those subjects who have a CR or PR.

Clinical benefit rate will be calculated as the number of subjects with confirmed CR, PR, or SD (where the duration of SD should be  $\geq 3$  months) divided by the total number of subjects in the Response Evaluable Population. The number and proportion of subjects with clinical benefit will be summarized.

The time to response will be summarized descriptively for subjects who have a CR or PR.

[REDACTED]

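### SAP 7 redefines the primary ORR population in two ways, while SAP 14 declares no change from the protocol

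*SAP*

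**What the plan says.** Protocol 10.4 defines the Response Evaluable Population as subjects with baseline measurable disease who have a post-baseline response assessment "or are withdrawn due to progressive disease/death prior to first response assessment". The statistical methods part of the synopsis repeats this: subjects must "have one post-baseline assessment of tumor response or are withdrawn due to progressive disease/death prior to first response assessment". The synopsis also requires receipt of study drug. Neither place requires that the entry criteria were met.

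Protocol 10.5.3 ties the primary endpoint to this set: "The primary efficacy measurement will be ORR per RECIST v1.1 based on the Response Evaluable population by tumor type". Its next sentence gives the denominator differently: "CR and PR) will be calculated based on number of subjects with measurable disease at baseline".

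SAP 7 keeps the population's name. It admits "subjects who met all eligibility criteria" who have measurable disease "at baseline, and also have at least one post-baseline assessment of tumor response", and the definition ends there. SAP 9.1 uses the set for best overall response (BOR), and SAP 9.2 uses it for ORR and clinical benefit rate (CBR). SAP 9.2 adds BOR and ORR in all treated subjects. SAP 14 states that the protocol's analyses are unchanged.

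For CBR the protocol is not consistent with itself. The synopsis, having placed ORR and BOR on the response evaluable set, says "Other secondary efficacy analyses will be based on the all treated population". Section 10.5.3 has CBR "divided by the total number of subjects in the Response Evaluable Population".

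**The concern.** ORR is the primary efficacy endpoint of a trial with no control arm, so the proportion and its exact interval are the efficacy result. SAP 7 changes who is counted, in two respects.

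First, it removes subjects who progressed or died before any assessment. They are certain non-responders, and the protocol clause exists to keep them in the denominator.

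Second, it removes treated and scanned subjects who turn out not to have met an entry criterion. Under SAP 8.2, protocol deviations are classified before database lock. In an open-label trial the responses can be known by then, so the exclusion is not protected from knowledge of outcome.

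A reader who takes SAP 14 at its word would believe the reported ORR is on the protocol's set. The Safety, DLT and Pharmacokinetic definitions in SAP 7 do match Protocol 10.4, which makes the departure in this one easy to miss.

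**Working it through.** **Definitions side by side**

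| Condition | Protocol 10.4 and synopsis | SAP 7 |
|---|---|---|
| Measurable disease at baseline | required | required |
| All eligibility criteria met | not required | required |
| Post-baseline assessment | required, or withdrawn for PD/death before it | required, no alternative |

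The protocol's one assessment versus the SAP's at least one makes no evident difference.

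**Inputs.** The documents give about 50 RCC subjects in the expansion phase (Protocol 10.2, SAP 4) and exact Clopper-Pearson 95% intervals (SAP 9.2). They give no target ORR, null rate or power, so there is no planned figure to reproduce. The following are assumptions: N = 50 in the protocol set; r = 10 responders; k subjects withdrawn for PD or death without a scan; m ineligible subjects, j of them responders.

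**Effect of the omitted clause alone.** ORR = r/(N − k), so the protocol estimate is multiplied by N/(N − k).

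| k | ORR | 95% CI | Change (points) |
|---|---|---|---|
| 0 | 10/50 = 20.0% | 10.0–33.7 | – |
| 1 | 10/49 = 20.4% | 10.2–34.3 | +0.4 |
| 2 | 10/48 = 20.8% | 10.5–35.0 | +0.8 |
| 3 | 10/47 = 21.3% | 10.7–35.7 | +1.3 |
| 5 (hypothetical) | 10/45 = 22.2% | 11.2–37.1 | +2.2 |
| 10 (hypothetical) | 10/40 = 25.0% | 12.7–41.2 | +5.0 |

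For other values of r at k = 3, the factor is 50/47 = 1.064: 5 responders go from 10.0% to 10.6%, and 15 responders from 30.0% to 31.9%.

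**Effect of the eligibility condition alone.** ORR = (r − j)/(N − m). With m = 2:

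- j = 0: 10/48 = 20.8%
- j = 1: 9/48 = 18.8%
- j = 2: 8/48 = 16.7%

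**Both changes.** ORR = (r − j)/(N − k − m).

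- k = 3, m = 1: 10/46 = 21.7% (+1.7 points) if the ineligible subject did not respond, 9/46 = 19.6% (−0.4) if that subject did.
- k = 1, m = 2: 10/47 = 21.3% (+1.3) if neither responded, 8/47 = 17.0% (−3.0) if both did.

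**The protocol's two denominators.** Take 50 treated subjects, all eligible and with measurable disease, of whom 2 are unscanned for other reasons and 1 is an unscanned PD or death. Counting everyone with baseline measurable disease gives 10/50 = 20.0%. The Protocol 10.4 set drops the 2: 10/48 = 20.8%. The SAP 7 set drops all 3: 10/47 = 21.3%.

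**The case against.** The best counter-argument is that the SAP already supplies a protocol denominator. Measurable disease is an inclusion criterion (Protocol 5.1, criterion 7). On the literal second sentence of 10.5.3, the ORR denominator is therefore essentially all treated subjects, and SAP 9.2 reports ORR on that basis. Early deaths and ineligible subjects all stay in it. This is true on that reading. But 10.5.3 and the synopsis both name the Response Evaluable Population for ORR, and SAP 9.2 offers the all-treated figure as an addition and not for CBR. It limits the harm without restoring the protocol's set.

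The omitted clause should also bite rarely. Entry requires a life expectancy above 12 weeks, a scan is due at end of treatment unless one was done within 4 weeks, and Protocol 6.4 continues imaging until PD even after treatment stops. A subject with radiographic PD before week 8 would normally have a post-baseline assessment and stay in the SAP set. The clause mainly protects against early death and unscanned clinical deterioration. This stands: k is probably small, and the k = 5 and k = 10 rows should carry no weight. Likewise, the −3.0 end needs both ineligible subjects to be responders.

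No decision depends on the figure. Protocol 10.1 makes all analyses descriptive, and the population counts in SAP 8.1 and the by-subject listings would allow reconstruction. That also stands, but only for a reader who knows the definition has changed.

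Finally, SAP 1 refers to a protocol dated 24 October 2016, and the date of the supplied protocol is not visible. The mismatch is established between the two documents as supplied. The CBR conflict lies within the protocol and is not caused by SAP 7.

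**Conclusion.** The concern holds. Against the protocol as supplied, SAP 7 alters the primary ORR population twice, and SAP 14 is wrong to report no change. The omitted clause can only raise ORR or leave it unchanged. The eligibility condition has no fixed direction, so neither does the net effect.

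With an assumed 10 responders in a protocol set of 50, the omitted clause is worth +0.4 to +1.3 points for k of 1 to 3, and the combined cases shown run from −3.0 to +1.7. The 95% interval is 23.7 points wide (33.7 − 10.0). The effect is on the estimate and its interval, not on an error rate or decision rule. This should be fixed, at moderate severity: the numerical shift is probably small, but it affects the primary endpoint and is undeclared.

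**What to change.** 1. In SAP 7, restore the protocol's alternative for subjects who "or are withdrawn due to progressive disease/death prior to first response assessment" and delete the eligibility condition.
2. In SAP 9.1 and 9.2, state that these subjects count as non-responders for ORR and stay in the BOR denominator, and name their BOR category. Confirm that the all-treated ORR is reported alongside with its Clopper-Pearson interval.
3. In Protocol 10.5.3, align the measurable-disease denominator with the Response Evaluable Population, the set that both 10.5.3 and the synopsis name for ORR.
4. For CBR, first reconcile the synopsis with 10.5.3, then apply the restored definition wherever that set is used.
5. If the sponsor wants to keep either SAP change, declare it in SAP 14 with the reason.

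The cost is a few words in SAP 7 and 9, one phrase in Protocol 10.5.3 and possibly a synopsis edit for CBR. The protocol edits go through the amendment process. No new data are needed. The reported ORR may move slightly, in either direction.

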8 PLANNED ANALYSES

The following summary will be performed based on the safety population unless otherwise specified.

8.1 Subject Disposition

The summary for subject disposition will include number of subjects enrolled, number of subjects in each study population, number of subjects who discontinue from study treatment and reason for discontinuation, and number of subjects who discontinue from study and reasons for study discontinuation.

All enrolled subjects will be included in the summary table. All disposition data will be provided in a listing.

8.2 Protocol Deviation

Protocol deviations will be classified as important or non-important and grouped into different categories/subcategories by study team prior to data base lock. The number and percentage of subjects in each protocol deviation category/subcategory will be summarized. All protocol deviations will be provided in a listing.

8.3 Demographic and Baseline Characteristics

Demographic variables will include age, gender, ethnicity, and race. Baseline characteristics will include the Eastern Cooperative Oncology Group (ECOG) performance status, height, weight, and calculated body mass index (BMI). All demographic and baseline characteristics will be summarized for the safety population.

Age will be calculated as:

$$(\text{Date of the informed consent signed} - \text{Date of birth}) / 365.25.$$

BMI will be calculated as:

$$\text{BMI (kg/m}^2\text{)} = \frac{\text{Weight (kg)}}{[\text{Height (m)}]^2},$$

All demographic and baseline characteristics data will be provided in a listing.

8.4 Cancer History

The summary for cancer history will include type of primary cancer, stage at initial diagnosis, time since initial diagnosis of primary cancer to date of informed consent, time since diagnosis of metastatic disease or most recent local recurrence to date of informed consent, current status, stage at most recent recurrence. Incomplete date of initial diagnosis of primary cancer and diagnosis of metastatic disease or most recent local recurrence will be imputed using rules specified in Section 6.

All cancer history data will be provided in a listing.

8.5 Medical History

All medical history and surgery procedures prior to study enrollment will be coded by the Medical Dictionary for Regulatory Activities (MedDRA) and summarized by system organ class (SOC) and preferred term (PT). Subjects will be counted only once within each SOC and PT.

All medical history data will be provided in a listing.

8.6 Prior Therapy

All prior systemic therapies will be coded by the World Health Organization Drug Dictionary Enhanced (WHODDE) using the Anatomical Therapeutic Chemical (ATC) Classification System level 2 term (therapeutic main group) and PT. If the level 2 term is missing, then the level 1 term (anatomical main group) will be used. The number and percentage of subjects will be summarized by ATC level 2 term and PT. Subjects will be counted only once within each ATC level 2 term and PT.

The type of prior therapies, time since the last prior systemic therapy to date of informed consent, and total number of prior systemic therapies will be summarized. For the last prior therapy, the best response and the duration of the therapy will be summarized by ATC level 2 term and overall. For last systemic therapy with complete missing start date, duration of the therapy will not be calculated. Otherwise, partial start date will be imputed as specified in Section 6.

All prior cancer therapies including systemic therapy, surgery, and radiotherapy will be provided in a listing.

8.7 Prior and Concomitant Medications and Procedures

All medications will be coded by the WHODDE using ATC level 2 term (therapeutic main group) and PT. If the level 2 term is missing, then the level 1 term (anatomical main group) will be used.

Prior medications are defined as medications with stop date prior to the first dose. Concomitant medications are defined as medications with stop date after the date of first dose. Medications with incomplete stop date will be imputed by rules specified in Section 6. The number and percentage of subjects who have concomitant medications will be summarized by ATC level 2 term and PT. Subjects will be counted only once under each ATC level 2 term and PT.

All procedures performed prior and during the study will be coded by MedDRA using SOC and PT. Only procedures performed after the date of first dose will be summarized. The number and percentage of subjects who have procedures performed after the date of first dose will be summarized by SOC and PT. Subjects are counted once in each SOC and PT.

All prior and concomitant medications and procedures will be provided in a listing.

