5 GENERAL ANALYSIS CONSIDERATIONS AND DEFINITIONS

The statistical analyses will be reported using summary tables, figures, and data listings. Unless otherwise specified, data collected during the dose escalation phase will be presented by dose cohort and overall. Data collected during the dose expansion phase will be presented by tumor type and overall.

Summary statistics for continuous variables will include the mean, standard deviation, median, minimum, and maximum. The mean will be presented to one decimal place beyond which the data were captured. The standard deviation will be presented to two decimal places beyond which the data were captured. The minimum and maximum will be presented to the precision with which the data were captured.

Categorical variables will be presented as frequency counts and percentages. A row or column denoted 'Missing' will be included in count tabulations where necessary to account for dropouts and missing values. Percentages will be rounded to 1 decimal place and the percent will be suppressed when the count is zero. The denominator will be the number of subjects in that dose cohort within the population of interest unless otherwise noted.

Time-to-event variables will be analyzed using the Kaplan-Meier method. The number and percentage of subjects with events or censored will be presented. The Kaplan-Meier estimates for quartiles (i.e., 25%, median, and 75%) and the 95% confidence interval for the median will be presented. All time to event variables will be plotted using the Kaplan-Meier method.

All data, including data collected from the electronic case report form (eCRF) and derived for statistical analysis, will be listed.

Cycle 1/Day 1 (C1D1) is defined as the first day of study treatment administration. Other study days will be calculated as follows:

- for any date post the date of C1D1:
Study day = visit date – date of C1D1 + 1
- for any date prior to the date of Cycle 1/Day 1:
Study day = visit date – date of C1D1

Unless otherwise specified, the baseline is defined as the last non-missing value prior to C1D1.

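### SAP medication rules leave a stop on the first dose date unclassified, label year-only stops in the first-dose year as prior, and allow negative durations for the last systemic therapy

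*SAP*

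**What the plan says.** SAP 8.7 gives two definitions, both based on the stop date only: "Prior medications are defined as medications with stop date prior to the first dose" and "Concomitant medications are defined as medications with stop date after the date of first dose". SAP 5 fixes the reference date: "Cycle 1/Day 1 (C1D1) is defined as the first day of study treatment administration".

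SAP 6 opens with "No imputation will be considered for incomplete data except the following". For medication stop dates it then sets these rules, whose stated purpose is the prior/concomitant classification:

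- Year missing: "If the year is missing, then the stop date will not be imputed".
- Day missing, in the month of C1D1: "then the stop date will be imputed as the date of C1D1".
- Day missing, in an earlier month: the first of that month.
- Only the year known, an earlier year: 1 July.
- Only the year known, the C1D1 year: "otherwise if the year is the same as the year of C1D1, then the stop date will be imputed as 01/January".

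For the last systemic therapy, SAP 6 treats a year-only start as follows: "if the year is prior to the year of informed consent, then the start date will be imputed as 01/July". A year-only stop in a year before consent also becomes 1 July, and one in the consent year becomes 1 January. A stop with only the day missing becomes the first of the month. SAP 8.6 summarizes the duration of that therapy.

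Protocol 6.13 collects medications from Screening through the end-of-treatment visit, and Protocol 10.6 requires concomitant medications to be tabulated. Neither says where prior ends and concomitant begins.

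**The concern.** A classification rule should place every record in one class, and an imputation rule written to support it should not produce a date that the classification cannot handle. Here the same-month rule does produce such a date. The 1 January rule has a different fault. It always resolves an ambiguous stop in the same direction, towards prior, although the drug may have been started or stopped after dosing began.

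The records exposed to the Day 1 gap include supportive drugs whose only use ended on the first dosing day. Protocol 6.3 and 6.11 foresee drug treatment around dosing, for example anti-emetics and vasopressors, and safety and tolerability is a primary objective. A table of concomitant medication should show such use.

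For the last systemic therapy, a start imputed without reference to the stop, or a stop imputed without reference to the start, can reverse their order and put impossible values into the duration summary.

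**Working it through.** The plan states no figure on this point, so there is none to reproduce. The check applies the rules literally to test dates. Assumed for illustration: C1D1 = 15 June 2016, informed consent = 20 May 2016.

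**Medications** (prior if stop < C1D1; concomitant if stop > C1D1)

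| Stop as recorded | Date after SAP 6 | Class under SAP 8.7 |
|---|---|---|
| 14 Jun 2016 | unchanged | prior |
| 15 Jun 2016 | unchanged | neither |
| 16 Jun 2016 | unchanged | concomitant |
| Jun 2016, day missing | 15 Jun 2016 | neither |
| 2016 only | 1 Jan 2016 | prior |
| Aug 2016, day missing | no rule | not stated |
| 2017 only | no rule | not stated |
| ongoing, no stop date | not imputed | not stated |

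The second row needs no missing data: a complete and correct stop date on C1D1 falls between the two definitions. The fourth row shows the imputation moving partial dates onto that same gap. The fifth row does not depend on the chosen date: over the 366 possible C1D1 dates in 2016, a year-only 2016 stop is prior for 365 and unclassified for one (1 January).

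**Last systemic therapy** (stop minus start, in days)

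SAP 8.6 gives no duration formula. Adding one day, as SAP 10.2 does for adverse events, changes no sign below. The rows with a partial stop assume that the stop imputed in SAP 6 is also used for the duration, which the SAP does not say outright. The first row does not need that assumption.

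| Start recorded | Stop recorded | Dates used | Difference |
|---|---|---|---|
| 2015 only | 31 Mar 2015 | 1 Jul; 31 Mar | -(30 + 31 + 30 + 1) = -92 |
| 2015 only | Mar 2015 | 1 Jul; 1 Mar | -122 |
| 10 Sep 2015 | 2015 only | 10 Sep; 1 Jul | -(31 + 31 + 9) = -71 |
| 10 Feb 2016 | 2016 only | 10 Feb; 1 Jan | -(31 + 9) = -40 |
| 10 Apr 2015 | Apr 2015 | 10 Apr; 1 Apr | -9 |

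With a year-only start in a (non-leap) year before consent, any complete stop from 1 January to 30 June of that year reverses the order: 31 + 28 + 31 + 30 + 31 + 30 = 181 of 365 dates. That is a count of calendar dates, not an estimate of how often it will happen. The last three rows show that the fault runs both ways: there the start is known and the imputed stop falls before it.

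**The case against.** The strongest reply is that this is wording with little reach. The planned safety assessment rests on adverse events, laboratory tests, vital signs, ECG and echocardiogram, and physical examination, not on the medication table. Subjects are counted once per ATC term and preferred term, so a Day 1 drug that is used again later still appears. SAP 5 lists all collected data whatever the class. On-study drugs are recorded with start and stop dates under Protocol 6.13, so a stop known only to the year is more plausible for pre-study history. All of this stands and limits the size of the point. It does not make the stated rules correct.

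Two stronger readings are tempting, and the documents do not support them.

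- A reader might infer that every ongoing medication drops out of the concomitant table, because it has no stop date and none is imputed. A drug that has not stopped must stop, if ever, after the first dose, and the protocol requires concomitant medications to be tabulated, so a programmer would very likely count it as concomitant. The SAP lacks a clarifying phrase; it does not predict a loss. The same applies to partial stops in a month or year after C1D1.
- A reader might put a share on the mislabelled year-only stops. With C1D1 on 1 March and stops spread evenly over the year, 306/365 = 84% would fall on or after C1D1. Both assumptions are invented. The count also runs to 31 December although collection ends at the end-of-treatment visit, and the share moves with C1D1 from nearly all (early January) to almost none (late December).

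A fair objection to the remedy is that treating undetermined stops as concomitant swaps one misclassification for the opposite one. That is true, but SAP 6 already resolves adverse event stop dates towards the later date, and for a table describing on-study drug use that is the safer direction.

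**Conclusion.** The point holds as a minor one. On the literal text, a stop on C1D1 belongs to neither class; a stop with the day missing in the C1D1 month is imputed to that date; and a stop known only to the C1D1 year is labelled prior for any C1D1 after 1 January. These are faults in stated rules, not just missing detail, and nothing elsewhere in the protocol or SAP repairs them. Durations of the last systemic therapy can be negative, by -92 and -71 days in the main examples.

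The effect is confined to two descriptive outputs: the concomitant-medication table and the prior-therapy duration summary. No endpoint, dose decision or safety rule depends on them. The Day 1 gap needs only a complete stop date; the other faults need partial dates, whose frequency the documents do not give.

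**What to change.** In SAP 8.7, define prior as a stop date, complete or partial, that is determinably before C1D1. Define concomitant as a stop on or after C1D1, an ongoing drug, or a stop that cannot be determined to be before C1D1. Every record then has exactly one class.

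In SAP 6, delete the 1 January and C1D1 stop-date imputations used for this classification; the new definitions make them unnecessary. A partial stop in an earlier month or year remains determinably prior.

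For the last systemic therapy, constrain imputed dates in both directions, keeping the known parts of each date: an imputed start no later than the stop, and an imputed stop no earlier than the start. Capping only the start would leave the -71, -40 and -9 day cases. State whether the imputed stop is used for the duration. While editing, correct the start-date rule, which twice names the stop date.

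The cost is a few sentences and no new data. The downside is that some truly prior drugs with partial stop dates will be counted as concomitant; a table footnote can say so.
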